9.4 Safety Analysis

All safety analyses will be based on data from the TE period for all subjects in the Safety Set, unless otherwise specified. Subjects will be analyzed according to the treatment they actually received in the Treatment Period. For subjects receiving study drug from more than one treatment group, the treatment group allocation will be ELX/TEZ/IVA.

The overall safety profile of study drug will be assessed in terms of the following safety and tolerability assessments:

- Treatment-emergent adverse events (TEAEs)
- Clinical laboratory values
- ECGs
- Vital signs
- Pulse oximetry

Only descriptive analysis of safety will be performed, and no statistical testing will be performed.

9.4.1 Adverse Events

For analysis purposes, AEs will be classified as pretreatment AEs, TEAEs, or post-treatment AEs, defined as follows:

Pretreatment AE: any AE that occurred before the first dose date of study drug

TEAE: any AE that worsened (either in severity or seriousness) or that was newly developed at or after the first dose date of study drug through the end of the TE period

Post-treatment AE: any AE that worsened (either in severity or seriousness) or that was newly developed after the TE period

For AEs with completely missing or partially missing start dates, if there is no clear evidence that the AEs are pretreatment or post-treatment, the AEs will be classified as TEAEs.

Details for imputing missing or partial start dates of adverse events are described in [Appendix D](#).

An overview of all TEAEs by treatment group and overall will be summarized in the following categories:

- Number of TEAEs

- Subjects with any TEAEs
- Subjects with TEAEs by strongest relationship
- Subjects with TEAEs by maximum severity
- Subjects with TEAEs leading to study drug discontinuation
- Subjects with TEAEs leading to study drug interruption
- Subjects with Grade 3/4 TEAEs
- Subjects with related TEAEs
- Subjects with serious TEAEs
- Subjects with related serious TEAEs
- Subjects with TEAEs leading to death

The following summary tables of TEAEs will be presented by MedDRA System Organ Class (SOC) and Preferred Term (PT) using frequency counts and percentages (i.e., number and percentage of subjects with an event), and by treatment group:

- All TEAEs
- Grade 3/4 TEAEs
- TEAEs by strongest relationship
- TEAEs by maximum severity
- TEAEs leading to treatment discontinuation
- TEAEs leading to treatment interruption
- Related TEAEs
- Serious TEAEs
- Related serious TEAEs
- TEAEs leading to death

When summarizing the number and percentages of subjects, subjects with multiple occurrences of the same adverse event or a continuing adverse event will be counted once, and only the maximum severity level will be presented in the severity summaries, and the strongest relationship level in the relationship summaries.

All AEs, including pretreatment AEs, TEAEs, and post-treatment AEs, will be presented in an individual subject data listing based on the All Subjects Set. In addition, listings containing individual subject adverse event data for TEAEs leading to treatment discontinuation, TEAEs leading to treatment interruption, Grade 3/4 TEAEs, SAEs and all deaths will be provided separately, with a flag indicating the TEAE status for SAEs and deaths.

9.4.1.1 Adverse Events of Special Interest

For this study, elevated transaminase events and rash events, as determined by MedDRA preferred terms in [Appendix F](#), are considered as adverse events of special interest.

For treatment-emergent elevated transaminase events and rash events, the following categories will be summarized by treatment group:

- Subjects with events

- Subjects with events by maximum severity
- Subjects with events leading to treatment discontinuation
- Subjects with events leading to treatment interruption
- Subjects with serious events
- Subjects with related serious events
- Subjects with events leading to death
- Duration of events
- Time-to-onset of first event

9.4.2 Clinical Laboratory

For the treatment-emergent laboratory measurements, the observed values and change from baseline values of the continuous hematology, serum chemistry, and coagulation results will be summarized in SI units by treatment group at each visit.

The number and percentage of subjects meeting at least 1 threshold analysis criterion, during the TE period, will be summarized by treatment group. The threshold analysis of shift from baseline will also be summarized for LFT laboratory parameters. The threshold analysis criteria are provided in [Appendix E](#).

For selected LFT laboratory tests (alanine transaminase [ALT], aspartate transaminase [AST], alkaline phosphatase [ALP], and total bilirubin), a scatter plot of the maximum treatment-emergent value versus the baseline value corresponding to \times ULN (upper limit of normal) will be presented by treatment group. Further, a scatter plot of the maximum treatment-emergent value of ALT and AST, separately, versus the maximum treatment-emergent value of total bilirubin corresponding to \times ULN will also be presented by treatment group.

Results of urinalysis and positive urine/serum pregnancy test will be listed in individual subject data listings only. For positive serum pregnancy listing, subjects with serum HCG which are abnormally high will be selected.

In addition, a listing containing individual subject hematology, chemistry, and coagulation values will be provided. This listing will include data from both scheduled and unscheduled visits.

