8.2 Exclusion Criteria

1. History of any illness or any clinical condition that, in the opinion of the investigator, might confound the results of the study or pose an additional risk in administering study drug(s) to the subject. This includes, but is not limited to, the following:
 - Clinically significant liver cirrhosis with or without portal hypertension
 - Solid organ or hematological transplantation

- Alcohol or drug abuse in the past year, including, but not limited to, cannabis, cocaine, and opiates, as deemed by the investigator
 - Cancer, except for squamous cell skin cancer, basal cell skin cancer, and Stage 0 cervical carcinoma in situ (all 3 with no recurrence for the last 5 years)
2. Any clinically significant laboratory abnormalities at the Screening Visit that would interfere with the study assessments or pose an undue risk for the subject (as deemed by the investigator).
 3. Any of the following abnormal laboratory values at screening:
 - Hemoglobin <10 g/dL
 - Total bilirubin $\geq 2 \times$ upper limit of normal (ULN)
 - Aspartate transaminase (AST), alanine transaminase (ALT), gamma-glutamyl transferase (GGT), or alkaline phosphatase (ALP) $\geq 3 \times$ ULN
 - Abnormal renal function defined as glomerular filtration rate $\leq 45 \text{ mL/min/1.73 m}^2$ (calculated by the Counahan-Barratt equation)¹³
 4. An acute upper or lower respiratory infection, pulmonary exacerbation, or changes in therapy (including antibiotics) for pulmonary disease within 28 days before Day 1 (first dose of study drug).
 5. Lung infection with organisms associated with a more rapid decline in pulmonary status (including, but not limited to, *Burkholderia cenocepacia*, *Burkholderia dolosa*, and *Mycobacterium abscessus*). For subjects who have had a history of a positive culture, the investigator will apply the following criteria to establish whether the subject is free of infection with such organisms:
 - The subject has not had a respiratory tract culture positive for these organisms within the 12 months before the date of informed consent.
 - The subject has had at least 2 respiratory tract cultures negative for such organisms within the 12 months before the date of informed consent, with the first and last of these separated by at least 3 months, and the most recent one within the 6 months before the date of informed consent.
 6. An acute illness not related to CF (e.g., gastroenteritis) within 14 days before the first dose of study drug (Day 1).

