9 STATISTICAL ANALYSIS

9.1 General Considerations

Continuous variables will be summarized using the following descriptive summary statistics: the number of subjects (n), mean, SD, median, minimum value (min), and maximum value (max).

Categorical variables will be summarized using counts and percentages.

Baseline value, unless otherwise specified, will be defined as the most recent non-missing measurement (scheduled or unscheduled) collected before the first dose of study drug in the Treatment Period.

Absolute change from baseline will be calculated as post-baseline value – baseline value.

Relative change from baseline will be calculated as (post-baseline value – baseline value)/baseline value.

Treatment-emergent (TE) Period will include the time from the first dose date of study drug to 28 days after the last dose of the study drug or to the date of completion of study participation, whichever occurs first.

Unscheduled visits: Unscheduled visit measurements will be included in analysis as follows:

- 1) In scheduled visit windows per specified visit windowing rules
- 2) In the derivation of baseline and last on-treatment measurements
- 3) In the derivation of maximum and minimum values during TE period, and maximum and minimum change from baseline values during TE period for safety analyses
- 4) In individual subject data listings as appropriate

Visit windowing rules: The analysis visit windows for protocol-defined visits are provided in [Appendix A](#).

Incomplete/missing data will not be imputed, unless specified otherwise.

Outliers: No formal statistical analyses will be performed to detect or remedy the presence of statistical outliers, unless specified otherwise.

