9.4.4 Vital Signs

For the treatment-emergent vital signs measurements, the observed values and change from baseline values will be summarized at each visit by treatment group. The following vital signs parameters will be summarized: weight (kg), weight-for-age z-score, height (cm), height-for-age z-score, BMI (kg/m²), BMI-for-age z-score, systolic and diastolic blood pressure (mm Hg), body temperature (°C), pulse rate (beats per minute), and respiratory rate (breaths per minute).

The number and percentage of subjects meeting at least 1 threshold analysis criterion during the TE period will be summarized by treatment group. The threshold analysis criteria are provided in [Appendix E](#).

In addition, a listing containing individual subject vital signs values will be provided. This listing will include data from both scheduled and unscheduled visits.

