Appendix E: Criteria for Threshold Analysis

Table 12-3 Threshold Analysis Criteria for Laboratory Tests (as applicable)

Parameter	Threshold Analysis	Comments
Clinical Chemistry (LFT)		
ALT	>ULN - ≤3xULN >3x - ≤ 5xULN >5x - ≤ 8xULN >8x - ≤ 20xULN >20xULN	FDA DILI Guidance Jul 2009.
AST	>ULN - ≤3xULN >3x - ≤ 5xULN >5x - ≤ 8xULN >8x - ≤ 20xULN >20xULN	FDA DILI Guidance Jul 2009.
ALT or AST	(ALT>ULN - ≤ 3xULN) or (AST>ULN - ≤ 3xULN) (ALT>3x - ≤ 5xULN) or (AST>3x - ≤ 5xULN) (ALT>5x - ≤ 8xULN) or (AST>5x - ≤ 8xULN) (ALT>8x - ≤ 20xULN) or (AST>8x - ≤ 20xULN) ALT>20xULN or AST> 20xULN	FDA DILI Guidance
Alkaline Phosphatase	>ULN - ≤ 1.5xULN >1.5x - ≤ 2.5xULN >2.5x - ≤ 5xULN >5x - ≤ 20xULN >20xULN	FDA DILI Guidance Jul 2009.
Total Bilirubin	>ULN - ≤ 1.5xULN >1.5x - ≤ 2xULN >2x - ≤ 3xULN >3x - ≤ 10xULN >10xULN	FDA DILI Guidance Jul 2009.
Direct Bilirubin	>ULN - ≤ 1.5xULN >1.5x - ≤ 2xULN >2x - ≤ 3xULN >3x - ≤ 10xULN >10xULN	FDA DILI Guidance Jul 2009.
Indirect Bilirubin	>ULN - ≤ 1.5xULN >1.5x - ≤ 2xULN >2x - ≤ 3xULN >3x - ≤ 10xULN >10xULN	FDA DILI Guidance Jul 2009.
ALT and Total Bilirubin	ALT>3xULN and TBILI>2xULN	FDA DILI Guidance Jul 2009.
AST and Total Bilirubin	AST>3xULN and TBILI>2xULN	FDA DILI Guidance Jul 2009.

Table 12-3 Threshold Analysis Criteria for Laboratory Tests (as applicable)

Parameter	Threshold Analysis	Comments
(ALT or AST) and Total Bilirubin	(ALT>3xULN or AST>3xULN) and TBILI>2xULN	FDA DILI Guidance Jul 2009.
GGT	>ULN - ≤ 2.5xULN >2.5x - ≤ 5xULN >5x - ≤ 20xULN >20xULN	CTCAE grade 1-4
Clinical Chemistry (NON-LFT)		
Albumin	<LLN - ≥ 30 g/L <30 - ≥ 20 g/L <20 g/L	CTCAE grade 1-3
Amylase	>1x - ≤ 1.5xULN >1.5x - ≤ 2xULN >2x - ≤ 5xULN >5xULN	Criteria based upon CTCAE
Creatinine	>ULN - ≤ 1.5xULN >1.5x - ≤ 3xULN >3x - ≤ 6xULN >6xULN	CTCAE grades 1-4
Lipase	>ULN - ≤ 1.5xULN >1.5x - ≤ 2xULN >2x - ≤ 5xULN >5xULN	Criteria based upon CTCAE
Total protein	<LLN >ULN	No CTCAE
Creatine kinase	>ULN - ≤ 2.5xULN >2.5x - ≤ 5xULN >5x - ≤ 10xULN >10xULN	CTCAE grades 1-4
Hematology		
Hemoglobin	Hgb decreased (anemia) <LLN - ≥ 100 g/L <100 - ≥ 80 g/L < 80 g/L	CTCAE grade 1-3
	Hgb increased >ULN - ≤ 20 g/L above ULN >20 g/L above ULN - ≤ 40 g/L above ULN >40 g/L above ULN	CTCAE grade 1-3
Platelets	Platelet decreased <LLN - ≥ 75 x 10e9 /L <75 - ≥ 50 x 10e9 /L <50 - ≥ 25 x 10e9 /L <25 x 10e9 /L	CTCAE grade 1-4
	Platelet increased >ULN	No CTCAE available

Table 12-3 Threshold Analysis Criteria for Laboratory Tests (as applicable)

Parameter	Threshold Analysis	Comments

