Reticulocytes/Erythrocytes (%)	<LLN >ULN	No CTCAE
Coagulation		
Activated partial thromboplastin time (PTT)	>ULN - $\leq 1.5 \times \text{ULN}$ >1.5x - $\leq 2.5 \times \text{ULN}$ >2.5xULN	CTCAE grade 1-3
Prothrombin time (PT) International Normalized Ratio (INR)	>ULN - $\leq 1.5 \times \text{ULN}$ >1.5x - $\leq 2.5 \times \text{ULN}$ >2.5xULN	CTCAE grade 1-3

Table 12-4 Threshold Analysis Criteria for ECGs

Parameter	Threshold Analysis	Comments
HR	Bradycardia ≤ 50 bpm	
	Tachycardia ≥ 140 bpm	
PR	≥ 200 ms and increase from baseline ≥ 20 ms	
QRS	≥ 120 ms	
QTc	Absolute values (ms) >450 ms (Male) or >470 ms (Female) ≥ 500 ms	To be applied to any kind of QT correction formula.
	Increase from baseline Increase from baseline 30-60 ms Increase from baseline >60 ms	

Table 12-5 Threshold Analysis Criteria for Vital Signs

Parameter	Threshold Analysis	Comments
Pulse Rate	Same as above in ECG category	
SBP	>120 mmHg < 70 mmHg	
DBP	>80 mmHg <50 mmHg	
Weight	Weight gain ≥ 5 % increase from baseline	CTCAE grade 1-3
	Weight loss ≥ 5 % decrease from baseline	CTCAE grade 1-3

Table 12-6 Threshold Analysis Criteria for Laboratory Tests

Parameter	Threshold Analysis	Comments
Clinical Chemistry (LFT)		
ALT or AST	>3xULN	
	>5xULN	
	>8xULN	

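### Outside the liver tests and oximetry, most absolute-limit threshold counts ignore baseline; a count of new or worsened abnormalities should be added beside them

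*SAP*

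**What the plan says.** For laboratory tests, SAP 9.4.2 states: "The number and percentage of subjects meeting at least 1 threshold analysis criterion, during the TE period, will be summarized by treatment group". SAP 9.4.4 repeats this for vital signs ("The number and percentage of subjects meeting at least 1 threshold analysis criterion during the TE period will be summarized by treatment group"), and 9.4.3 uses the same sentence for ECG. The TE period is a time window: it "will include the time from the first dose date of study drug to 28 days after the last dose of the study drug", unless study participation ends sooner. It puts no worsening condition on measurements.

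The criteria are in SAP Appendix E, Tables 12-3 to 12-5. Some take account of baseline:

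- The PR row requires a limit in "ms and increase from baseline" of at least 20 ms.
- Two QTc rows are defined by the increase alone.
- The weight rows are percentage changes from baseline.

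The rows for non-liver chemistry, hematology, coagulation, heart and pulse rate, QRS, absolute QTc, SBP and DBP have only absolute or reference-range limits.

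Shift analysis of laboratory data is confined to the liver tests: "The threshold analysis of shift from baseline will also be summarized for LFT laboratory parameters". SAP 9.4.5 gives pulse oximetry its own shift table. Protocol 12.3.4.2 had left the choice of shift parameters to the SAP.

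**The concern.** A threshold table by arm is normally read as showing what happened on treatment. In the rows without a baseline term, it also includes what the child brought into the study.

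Hemoglobin is the clearest case. The numeric entry limit in Protocol 8.2 is "Hemoglobin <10 g/dL", that is, 100 g/L. The mildest band in Appendix E, under a label that begins "Hgb decreased (anemia", runs from the lower limit of normal down to 100 g/L. A child can therefore enter inside that band. The child is then tabulated under a decrease if hemoglobin stays there, or if it rises but some value on study is still below the lower limit of normal.

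Protocol 8.2 states no numeric limit for creatine kinase, lipase, amylase, platelets, coagulation or blood pressure, so the same can happen in those rows.

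Safety is a secondary objective and is assessed descriptively only, so readers will compare these percentages by eye. Events that are not new raise both percentages, pull their ratio toward 1 and add noise to their difference. The SAP follows the opposite principle elsewhere: in 9.4.1 a TEAE must be new or worsened.

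**Working it through.** The documents state no figure for the threshold tables, so there is none to reproduce. The only design figure used is the arm size: about 108 children randomized 1:1, so 108/2 = 54 per arm (SAP 7.1).

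The other inputs are assumptions, because the documents give no values:

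- q, the share already past a limit at baseline: 0%, 5%, 10% or 20%, equal in both arms by randomization.
- r, the share of those with a value still past the limit on study: 1.0 or 0.7, the same in both arms.
- p, new onset among children normal at baseline: 5% on placebo, 15% on drug.
- Children abnormal at baseline do not move into a worse band.

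Formulas, per arm:

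- Any-time count (SAP rule): q·r + (1−q)·p
- New-or-worsened count: (1−q)·p
- Risk difference under either rule: (1−q)·(0.15 − 0.05), because q·r cancels
- SE of the difference: √[Σ rate·(1−rate)/54], summed over the two arms

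Worked case, q = 10% and r = 1:

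- Any-time: placebo 0.10 + 0.90×0.05 = 14.5%; drug 0.10 + 0.90×0.15 = 23.5%. Ratio 1.62, difference 9.0 points.
- New or worsened: 0.90×0.05 = 4.5%; 0.90×0.15 = 13.5%. Ratio 3.0, difference 9.0 points.
- Share of any-time events that are not new: 0.10/0.145 = 69% on placebo, 0.10/0.235 = 43% on drug.
- SE, any-time: √[(0.145×0.855 + 0.235×0.765)/54] = 0.0750, so difference/SE = 1.20.
- SE, new or worsened: √[(0.045×0.955 + 0.135×0.865)/54] = 0.0544, so difference/SE = 1.65.

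All cases (placebo vs drug):

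| q | Any-time, r = 1 | Ratio | Any-time, r = 0.7 | Ratio | New or worsened | Ratio | Difference (points) |
|---|---|---|---|---|---|---|---|
| 0% | 5% vs 15% | 3.0 | 5% vs 15% | 3.0 | 5% vs 15% | 3.0 | 10.0 |
| 5% | 9.75% vs 19.25% | 1.97 | 8.25% vs 17.75% | 2.15 | 4.75% vs 14.25% | 3.0 | 9.5 |
| 10% | 14.5% vs 23.5% | 1.62 | 11.5% vs 20.5% | 1.78 | 4.5% vs 13.5% | 3.0 | 9.0 |
| 20% | 24% vs 32% | 1.33 | 18% vs 26% | 1.44 | 4% vs 12% | 3.0 | 8.0 |

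For q = 5%, 10% and 20% with r = 1, difference/SE is 1.41, 1.20 and 0.93 for the any-time count. For the new-or-worsened count over all 54 per arm it is 1.71, 1.65 and 1.55. The loss is about 17%, 27% and 40%. These ratios describe precision only; the plan tests no safety comparison.

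The difference falls from 10.0 to 8.0 points down the table because fewer children are at risk of new onset. In each row it is the same under both rules.

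**The case against.** The case for leaving the plan alone has substance. The SAP made a selection that the protocol handed to it, so there is no contradiction between the documents. Baseline is also considered elsewhere. SAP 9.4.2 provides that "the observed values and change from baseline values of the continuous hematology, serum chemistry, and coagulation results will be summarized in SI units" at each visit; 9.4.3 and 9.4.4 do likewise for ECG and vital signs, and all three add subject listings. Clinically significant worsening in laboratory tests, ECGs and vital signs is documented as an AE (Protocol 13.1.1.2) and reaches the TEAE tables. Exclusion 2 in Protocol 8.2 lets the investigator keep out children with clinically significant laboratory abnormalities, which bears on any example of a grossly abnormal entry value. The hemoglobin bands are marked as CTCAE grades, so the label may name a scale and not claim a measured fall.

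These are only partial safeguards. By-visit change summaries describe groups and do not show how many children moved to a worse category. Listings need counting by hand. AE reporting and exclusion 2 rest on investigator judgement.

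A reader might infer that the threshold tables disregard baseline throughout, or that the rule shrinks the absolute difference between arms. The documents do not support the first: the PR, QTc-increase and weight rows use baseline, and liver tests and oximetry have shift tables. The arithmetic does not support the second when persistence is equal in the two arms. Nor are all hemoglobin bands affected alike. Because values below 100 g/L at screening are excluded, the two lower bands should hold largely new events.

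**Conclusion.** The point holds as a minor gap in reporting. For the non-liver absolute-limit rows, children past a limit at baseline who do not worsen, or who improve but stay in an abnormal band, are tabulated as threshold events.

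The size depends on how many children enter abnormal, which the documents do not say. Under the stated assumptions, with 5% to 20% abnormal at baseline, a true ratio of 3.0 is shown as 1.97 to 1.33 with full persistence, or 2.15 to 1.44 with 70% persistence. With none abnormal at baseline the two rules agree. The expected risk difference does not change but is less precisely estimated. That result rests on equal persistence in the two arms; unequal persistence would add q × (r on drug − r on placebo) to the any-time difference.

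No efficacy result and no hypothesis test is affected. The any-time count is a legitimate summary, but on its own it does not separate new from pre-existing abnormality.

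**What to change.** In SAP 9.4.2 to 9.4.4, keep the any-time counts. Beside them, for the non-liver absolute-limit rows of Appendix E Tables 12-3 to 12-5, add the number and percentage of subjects whose worst TE-period category is worse than their baseline category. Equivalently, extend the liver-test shift table to these parameters. Two definitions are needed:

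- Direction: assess high and low separately where a parameter has limits on both sides (hemoglobin, platelets, total protein, reticulocytes, heart and pulse rate, SBP, DBP).
- Missing baseline: treat it as normal, as SAP 9.4.5 does for oximetry.

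The PR, QTc-increase, weight and liver-test rows stay as they are.

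The cost is SAP wording and a few more descriptive tables. No new data are needed: SAP 9.1 already provides for baseline and for maximum and minimum TE-period values. No protocol change is required, since Protocol 12.3.4.2 leaves the selection of laboratory shift parameters to the SAP.

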9.4.3 Electrocardiogram

For the treatment-emergent ECG measurements, a summary of observed values and change from baseline values will be provided at each visit by treatment group for the following ECG interval measurements (in msec): RR interval, PR interval, QT interval, QTcF interval, QRS duration, and Heart Rate (beats per minute).

The number and percentage of subjects meeting at least 1 threshold analysis criterion during the TE period will be summarized by treatment group. The threshold analysis criteria are provided in [Appendix E](#).

In addition, a listing containing individual subject ECG values will be provided. This listing will include data from both scheduled and unscheduled visits.

9.4.4 Vital Signs

For the treatment-emergent vital signs measurements, the observed values and change from baseline values will be summarized at each visit by treatment group. The following vital signs parameters will be summarized: weight (kg), weight-for-age z-score, height (cm), height-for-age z-score, BMI (kg/m²), BMI-for-age z-score, systolic and diastolic blood pressure (mm Hg), body temperature (°C), pulse rate (beats per minute), and respiratory rate (breaths per minute).

The number and percentage of subjects meeting at least 1 threshold analysis criterion during the TE period will be summarized by treatment group. The threshold analysis criteria are provided in [Appendix E](#).

In addition, a listing containing individual subject vital signs values will be provided. This listing will include data from both scheduled and unscheduled visits.

